13.1 Primary endpoint: AUCs of CombiWISE scores

13.1.1 Primary analysis

The AUCs of the CombiWISE scores will be analyzed using an Analysis of Covariance (ANCOVA) model with the AUC of the pre-treatment CombiWISE scores, Baseline (Month 0) CombiWISE score and Baseline (Month 0) age as covariates.

The incomplete data in the CombiWISE scores during the 2-year treatment period will be managed with the single imputation algorithm defined in Section 4.2.

In addition to the primary analysis comparing the between-group difference, the within group changes will be tested using paired t-test within each treatment group. The t-tests will be based on Satterthwaite's approximation.

The analyses will be conducted both using the ITT population (primary) and Completer population (secondary).

13.1.2 Sensitivity analyses

The following sensitivity analyses will be conducted using the ITT population.

- Random coefficient regression model: random coefficient regression model with random intercept and slope will be fitted to the response data. All CombiWISE scores will be included as response variables in the model. In order to model random intercept and slope for pre-and post-treatment separately, factor period (pre vs. post) will be created: pre-treatment (Month -12 to 0) vs. post-treatment (Month 0 (+1 day) to 24). Exact clinic dates for each patient will be used as Time in the model. In addition to the random slopes and intercepts, the model will include the fixed effect for treatment group (idebenone or placebo), period (nested within treatment), interaction between Month and period (nested in treatment) and covariates: Baseline (Month 0) CombiWISE score and Baseline age. The effect of treatment and period (nested within treatment) factors will be used to examine the hypothesis of four intercepts are same (intercepts for placebo group at pre- and post-treatment, intercepts for idebenone group at period pre- and post-treatment). The interaction between Time and period (nested within treatment) will be used to examine the hypothesis of four slopes are same (slopes for placebo group at pre- and post-treatment, slopes for idebenone group at period pre-and post-treatment). This analysis includes only the observed CombiWISE scores as response variables and as the model can manage incomplete data, no imputation will be done.
- Mixed Model for Repeated Measures (MMRM): The change from Baseline to Month 24 in the CombiWISE scores will be compared between the idebenone and placebo groups using MMRM. The observed CombiWISE scores at Months 6, 12, 18 and 24 will be used as response variables in the MMRM. The treatment group, visit and interaction between treatment group and visit will be included as fixed factors. The pre-treatment slope (calculated with linear regression for each patient) and the baseline CombiWISE score will be included as covariates. An unstructured covariance structure will be applied for MMRM. The denominator degrees of freedom will be computed using the Kenward-Roger method. The difference between the groups at Month 24 (and at the other post-baseline visits) and within-group changes within each group will be estimated from the MMRM.
- Multiple Imputation (MI) assuming data missing at random (MAR) will be done to compare idebenone to placebo. MI techniques based on Pattern Mixture Models (PMM) will be applied in this sensitivity analysis. This methodology will structure data based on the missing data patterns. The method will be based on a missingness pattern having a monotone structure, i.e. if among the observations during the 2-year treatment period one CombiWISE score is missing, all subsequent scores after this missing value will also be treated as missing. For patients with intermittent missing values, before performing MI based on the PMM, it will be necessary to

create a monotone missingness pattern. Intermittent missing values will be imputed using the Markov Chain Monte Carlo (MCMC) methodology which assumes a multivariate normal distribution over all variables included in the imputation model. This first MI step is planned to be repeated 1000 times, creating 1000 different datasets with a monotone missing data structure. Seed value of 1995 will be used in the MI procedure. The imputation is based on the missing at random (MAR) assumption, i.e. the missing data are assumed to follow the same model as the other patients in their respective treatment arm.

After this, the remaining missing data will be imputed using a method for monotone missingness, also based on the MAR assumption. Thus, for each of the 1000 created dataset with a monotone missing data pattern, missing values will be imputed based on a sequential procedure reflecting the monotone missing data pattern. Patients with the first missing value occurring at Month 3 will have their missing Month 3 value replaced by an imputed value from a regression model with treatment group, Month 0 CombiWISE score, the pre-treatment slope and baseline age as explanatory variables. In the next step, patients with their Month 6 value missing will have their missing Month 6 value replaced by an imputed value from a regression model with all factors defined above and Month 3 value as explanatory variables. Similar procedure will be used to replace the missing values at all subsequent visits.

The imputed datasets generated with the approach described above do contain only non-missing values and are used as input in the model for the sensitivity analysis of the primary outcome variable. Random coefficient regression models similar as described in Sensitivity Analysis 1 will thus be run on each of the 1000 generated imputed datasets and the difference between the treatment groups will be estimated. Finally, the results from these analyses will be combined to derive an overall estimate of the treatment difference. In addition to the estimates, corresponding 95% confidence intervals and p-values will be calculated.

- Multiple Imputation assuming data missing not at random (MNAR) will be done to compare idebenone to placebo. Control group based assumption (Copy Reference imputation) will be used, i.e. the trajectories of the patients are assumed to follow the placebo group trajectories after the discontinuation. Methods similar to the procedure described above will be used to generate monotone missing data. After this, the missing data will be imputed sequentially for each visit (first Month 3, followed by all subsequent visits). Only the data from the control group (placebo group) will be used as input for each imputation of both treatment groups.

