1. Random coefficient regression model with random intercept and slope will be fitted to the response data. All CombiWISE scores will be included as response variables in the model. In order to model random intercept and slope for pre-and post-treatment separately, factor period (pre vs. post) will be created: pre -treatment (Month -12 to 0) vs. post-treatment (Month 0 (+1 day) to 24). Exact days from the first visit, instead of month will be used as Time in the model. In addition to the random slopes and intercepts, the model will include the fixed effect for treatment group (idebenone or placebo), period (nested within treatment), interaction between Time and period (nested in treatment) and covariates: Baseline (Month 0) CombiWISE score and Baseline age. The interaction between Time and period (nested within treatment) will be used to examine the hypothesis of four slopes are same (slopes for placebo group at pre- and post-treatment, slopes for idebenone group at period pre-and post-treatment). The pairwise comparisons of the four slopes or intercepts,

such as slope (or intercept) at post-treatment for idebenone group vs. that for placebo group, and slope (or intercept) for idebenone group at post-treatment vs. that at pre-treatment period can be constructed and performed using the statement “estimate”. This analysis includes only the observed CombiWISE scores as response variables and as the model can manage incomplete data, no imputation will be done.

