4.2 Primary efficacy endpoint

The primary endpoint of this study is the rate of disability progression, assessed with Area Under the Curve (AUC) of the CombiWISE scores during the 2-year treatment period. The CombiWISE data collected during the 1-year pre-treatment period will be utilized by including both the pre-treatment disability progression (AUC of CombiWISE scores during the pre-treatment period) and severity of the disability (CombiWISE score at pre-randomization baseline) as covariates in the statistical analysis.

Derivation of CombiWISE scores

CombiWISE is a combinatorial weight-adjusted disability score ranging from 0 to 100, where 0 represents no disability and 100 maximum disability. It was developed based on the pre-determined analysis of 58 candidate outcomes collected in 1 year pre-treatment phase in training (IPPOMS1) and validation (IPPOMS2 and RIVITALISE) cohorts, as described in detail in a recent publication (Kosa, Ghazali et al. 2016). The CombiWISE score is a composite of four scales: expanded disability status scale (EDSS), Scripps neurological rating scale (SNRS), 25 foot walk (25FW) and 9 hole peg test (9HPT) performed on non-dominant hand (NDH- 9HPT). The score is calculated with the following formula:

$$\begin{aligned} \text{CombiWISE} = & 33.166 + 3.803 \times \text{EDSS} - 0.407 \times \text{SNRS} + \\ & 2.409 \times \log(25\text{FW}) + 18.056 \times 25\text{FW}_{\text{fail}} + \\ & 1.305 \times \log(\text{NDH-9HPT}) + 10.751 \times \text{NDH}_{\text{fail}}. \end{aligned}$$

The components of the CombiWISE are derived as follows:

- EDSS: the EDSS score (scored as 1.0, 1.5, ..., 10.0) is recorded as such and requires no derivation.
- SNRS: the SNRS score, which can range between 100 (normal status) and 0 (worst possible score) is recorded as calculated by the investigator.
- $\log(25\text{FW})$ is \log_2 of the average of two attempts on 25FW, or 0 if at least one attempt is unsuccessful.
- $25\text{FW}_{\text{fail}}$ is 1 if patient failed either of the two attempts on 25FW; otherwise 0.
- $\log(\text{NDH-9HPT})$ is \log_2 of average of two attempts on 9HPT with non-dominant hand, or 0 if at least one attempt is unsuccessful.

- NDH_{fail} is 1 if patient failed either of the two attempts on 9HPT with non-dominant hand; otherwise 0.

Calculation of AUC values

The CombiWISE is assessed at the following time points:

- Pre-treatment baseline phase: Months -12, -6 and 0
- Double-blind phase: Months 6, 12, 18 and 24.

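### The random-coefficient sensitivity model regresses the Month 0 CombiWISE score on itself; depending on an unstated covariance structure, the standard error of its pre-versus-treatment slope contrast may be overstated by 0% to about 14%

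*SAP*

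**What the plan says.** SAP 13.1.2 describes the first sensitivity analysis of the primary endpoint as follows.

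- Responses: "All CombiWISE scores will be included as response variables in the model".
- Periods: "pre-treatment (Month -12 to 0) vs. post-treatment (Month 0 (+1 day) to 24". Month 0 therefore belongs to the pre-treatment period.
- Random effects: "In order to model random intercept and slope for pre-and post-treatment separately, factor period (pre vs. post) will be created".
- Covariates: "covariates: Baseline (Month 0) CombiWISE score and Baseline age".
- Slope test: "The interaction between Time and period (nested within treatment) will be used to examine the hypothesis of four slopes are same". A parallel joint test is planned for the four intercepts.

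SAP 4.2 gives the visits: "Pre-treatment baseline phase: Months -12, -6 and 0" and "Double-blind phase: Months 6, 12, 18 and 24". Month 0 is thus one of only three pre-treatment responses and one of seven in all.

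Protocol 11.2, sensitivity analysis 1, sets out the same model and adds that the "slope (or intercept) for idebenone group at post-treatment vs. that at pre-treatment period can be constructed".

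SAP 13.1.2 runs a similar model on each of the 1000 multiply imputed datasets. SAP 13.2 applies similar models to the continuous secondary endpoints other than neuroimaging.

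**The concern.** A baseline score is a proper covariate when every response comes after it. The MMRM in the same SAP section meets that condition: its responses are Months 6, 12, 18 and 24. The random-coefficient model does not, because the Month 0 score stands on both sides of the equation.

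The fit can then reproduce Month 0 almost perfectly, although the model assumes the same residual variance there as at every other visit. The Month 0 measurement error moves into the other visits. At stake are the standard error of the pre-treatment slope, hence the pre-versus-treatment comparison inside the four-slope test, and the meaning of the four-intercept test.

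**Working it through.** **Inputs from the documents.** Seven visits (Months -12, -6, 0, 6, 12, 18, 24), 33 patients per arm, and separate random intercepts and slopes by period. The plan states no standard error or variance component for this model, so there is no figure to reproduce. The SD of 46.2 and correlation of 0.5 in SAP 6.2 refer to the AUC and do not supply what is needed.

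**Assumed.** Residual SD σ = 1.5, intercept SD 12, slope SD τ from 0 to 2.5 times σ, pre/post slope correlation ρ from 0 to 1, complete data.

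**Step 1: the self-regression.** Let y₀ be a patient's Month 0 score and b its coefficient as a covariate. At Month 0 the part left to explain is y₀ − b·y₀ = (1 − b)·y₀, which is zero at b = 1. At any other visit, y − b·y₀ carries the Month 0 error with reversed sign. In large-sample calculations with period-specific random effects, b was 0.991 to 0.997. The model variance at Month 0 is the random-intercept variance there plus σ². Neither can be negative, so the fit lowers σ². The fitted residual SD was 1.34: 1.34² = 1.80 against 1.5² = 2.25, or 20% too low.

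**Step 2: slope estimates.** The term b·y₀ is the same at all of a patient's visits, so with complete data it cancels from within-patient slopes. The estimates are identical with and without the covariate.

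**Step 3: true variance of the slope change.** In years, the pre-treatment visits (-1, -0.5, 0) have sum of squares 0.5. The treatment visits (0.5, 1, 1.5, 2) have 1.25. Per patient:

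Var(change) = 2τ²(1 − ρ) + σ²/0.5 + σ²/1.25 = 2τ²(1 − ρ) + 4.5 + 1.8.

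**Step 4: one case in full.** Take τ = 0 and a non-negative-definite covariance. The true variance is 6.3, so the SE per arm is √(6.3/33) = 0.437. With the covariate, the model SE of the pre-treatment slope is 1.180 times its true value and that of the treatment slope 1.000 times. The model variance is 1.180² × 4.5 + 1.8 = 8.07, the SE is √(8.07/33) = 0.494, and the ratio is 0.494/0.437 = 1.13.

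**Step 5: range over the assumed values.** Change in model SE caused by the covariate:

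| Random-effects structure | Pre-versus-treatment contrast | Pre-treatment slope alone |
|---|---|---|
| Period-specific, 4×4 non-negative definite | +2.1% to +13.3% | +4.4% to +18.0% |
| Period-specific, periods independent | +2.4% to +14.1% | +4.5% to +19.3% |
| Period-specific, 4×4 unstructured, only variances bounded at 0 | 0% | 0% |

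Within the first row, the contrast is inflated by 9.4% at τ = σ, ρ = 0.5 and by 3.7% at τ = 2.5σ, ρ = 0.5. The second row compares the same model with and without the covariate. Assuming independent periods also overstates the SE when ρ > 0, but that is not due to the covariate. The treatment-period slope SE has ratio 1.00 in all three rows.

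**Step 6: check at the trial's size.** REML fits with the first structure (33 per arm, 120 fits in each of four scenarios, τ = 0.5σ to 1.0σ, ρ = 0.5 to 0.9) gave a contrast SE 9–10% larger with the covariate than without. Model SE over empirical SD was 1.13 with it and 1.03–1.04 without. Residual variance was 1.80–1.81 with it and 2.15–2.19 without, against a true 2.25.

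**Step 7: intercepts.** With time centred at Month 0 (an assumption), the between-arm pre-treatment intercept contrast had model SE 0.309 against an empirical SD of 0.162, a ratio of 1.91. Without the covariate the figures were 2.94 and 2.71. The drop from 2.94 to 0.309 shows the contrast being pulled to zero by adjusting the Month 0 level for itself. If time starts at the first visit, as Protocol 11.2 has it, the adjusted pre-treatment intercept is roughly minus the year's change, and so largely repeats the slope.

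**The case against.** The best defence is that little of consequence depends on this term. The model is a sensitivity analysis. The primary ANCOVA does not use it, the between-arm treatment-period slope contrast is essentially untouched, and any slope error is conservative. The SAP takes precedence over the protocol, and it drops the protocol's sentence on pairwise slope contrasts. It keeps the joint tests and tests within-arm change with a paired t-test in 13.1.1, which this covariate does not enter. All of that stands and limits the severity.

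A reader might infer that the error bars are too wide by a fixed amount, such as 9% to 18%. The documents do not support that. The result turns on variance components and a covariance structure they do not give. For the contrast the range is 0% to about 14%; 18% or more is reached only for the pre-treatment slope alone. One structure that fits the SAP's wording, the unstructured matrix bounded only on its variances, shows no inflation. A single intercept and slope per patient also shows essentially none (−0.4% to 0%), but it does not match the separate random effects that the SAP asks for.

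No figures were derived for EDSS, SNRS, 25FW or 9HPT, so the range should not be carried over to those endpoints.

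The defence does not remove the defect. Nothing in either document takes Month 0 out of the responses or out of the covariates, and the four-slope and four-intercept tests remain in the SAP.

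**Conclusion.** The specification is wrong as written, and the point is minor. The Month 0 score is both response and covariate, so the model is misspecified at that visit. Under the assumed variances and complete data, the model SE of the within-arm pre-versus-treatment slope contrast is overstated by 0% to about 14%, and the unstated covariance structure decides where in that range it falls. The joint four-slope test may therefore be conservative. The four-intercept test is distorted because the pre-treatment intercepts are adjusted for the Month 0 score itself.

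A reader might also infer that the treatment comparison is biased. It is not: complete-data slope estimates do not change, and the between-arm treatment-period slope contrast is not materially affected.

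**What to change.** Delete the Month 0 CombiWISE score from the covariates of the random-coefficient model in SAP 13.1.2, including its reuse after multiple imputation. Delete the corresponding baseline value from the similar models in SAP 13.2. Keep Month 0 as a response, where the random intercept carries the patient's level, and keep age. State the random-effects covariance structure and any bounds on it. In the large-sample calculation, dropping the term brought model SE over true SE for the slope contrast to 1.00 with the non-negative-definite structure; it was already 1.00 with the unstructured one.

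Removing Month 0 from the responses instead would be worse, since only Months -12 and -6 would remain to estimate the pre-treatment slope.

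The cost is one model term deleted and one sentence added. Since Protocol 7.6.10 reports that data analysis is complete, it also means rerunning any of these models already fitted.

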Figure 3: There are two possible ways how changes in outcomes collected every 6 months (e.g., primary outcome: CombiWISE) can be analyzed: 1. As a change in regression slopes (left panel) or 2. As a change in AUC (right panel). There are two major problems with regression slopes: First, the baseline pre-treatment period slope is derived only from 3 measurements. Because these measurements are spread equally apart, the least squares linear regression slopes are calculated only from 1st and 3rd measurement, whereas the middle (2nd) measurement affects only the intercept. Consequently, even though we have three baseline measurements, only two of them would be de-facto utilized for final outcome comparison. Furthermore, as depicted in the left panel, if the drug has both neuroprotective effect (which decreases slope) and promotes structural or functional repair (which decreases intercept), comparing slopes would de-facto ignore the latter potentially important mechanism of action (MOA). In contrast, measuring changes in disability progression between untreated and treated period using AUC (right panel) eliminates both stated disadvantages of progression slopes. This method uses all measured data and correctly deals with the improvements in disability by subtracting parts of the curve that are below the baseline (i.e. CombiWISE measure at the initiation of therapy) from the AUC part that is above the baseline.

The only problem with AUC is unequal length of the compared periods: while pre-treatment baseline period has 1-year length, the treatment period for IPPOMS trial has length of 2 years. It may be intuitive to divide 2-year AUC period by 2 to obtain equivalent yearly measurements, but that is incorrect. As depicted in the left panel, if the progression slopes were linear, the AUC derived from 2-year period needs to be divided by 4 to get equivalent yearly AUC progression. We have validated correctness of this adjustment by analyzing blinded 2 year CombiWISE data from 50 patients who finished 2 years of study and by comparing average AUC derived from splitting Year 1 and Year 2 of this longitudinal cohort, versus calculating AUC from the entire 2-year period. We observed that these two measurements strongly correlate with each other ($r^2=0.905$) with following linear regression formula:

$$Y = -0.77 + 3.96 * X, \text{ where } X \text{ is average yearly AUC and } Y \text{ is 2-year AUC measured in the same patient.}$$

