3.2 Adaption of objectives and endpoints

The study was planned to use an adaptive trial design. The trial started with a pre-treatment baseline period of at least 12 months, where magnetic resonance imaging (MRI), clinical and biomarker measurements were collected in all patients for two purposes:

- To obtain longitudinal quantitative MRI, clinical and electrophysiological data in untreated PP-MS patients before randomization. These data will be utilized for the selection of the most sensitive primary outcome measure. This will be done on the first 30 patients and subsequent analysis will be used for selection of the most sensitive primary outcome measure and for adjusting sample size calculation if the primary outcome measure is different than brain atrophy measured by SIENA methodology.
- To obtain patient-specific pre-randomization baseline for all collected outcome measures. This is expected to increase the statistical power of the study ((Murray et al. 2005, Young et al. 2005, Frost et al. 2008). In the study protocol, the following two assumptions were made: 1) CNS tissue destruction develops in a linear manner within a 3-5 year time-frame in the majority of PP-MS patients and 2) the slopes of the linear development of CNS tissue destruction differ among individual patients. Based on these two assumptions, the trial design will allow adjustment for the individualized rates of development of CNS tissue destruction.

The aim of the adaptive trial design was to allow the selection of the most robust (i.e. most sensitive and most accurate) primary outcome measure for the final analysis. Based on the analysis of the pre-treatment phase, the focus of the study shifted from the analysis based on MRI to analysis of clinical endpoints and composite scores. For more details, see section 6 of this SAP.

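### SAP sensitivity and secondary analyses: the intercept test has no time zero, baseline age is missing from the MMRM and Cox models, and neither multiple imputation re-estimates the primary AUC contrast

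*SAP*

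**What the plan says.** **Time.** For the random-coefficient model, SAP 13.1.2 states: "Exact clinic dates for each patient will be used as Time in the model". The slope term is then written as "interaction between Month and period (nested in treatment"), while the slope test is described with Time. For the intercepts: "The effect of treatment and period (nested within treatment) factors will be used to examine the hypothesis of four intercepts are same". No time zero appears. Protocol 11.2 (sensitivity analysis 1) does give one: "Exact days from the first visit, instead of month will be used as Time in the model". It adds that pairwise contrasts can be built, "such as slope (or intercept) at post-treatment for idebenone group vs. that for placebo group". The Figure 3 text in the same section considers what happens "if the drug has both neuroprotective effect (which decreases slope) and promotes structural or functional repair (which decreases intercept"). SAP 13.2 reuses the random-coefficient model for the continuous secondary endpoints other than neuroimaging, alongside an MMRM.

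**Age.** Protocol 7.4 stratifies randomisation on age alone (below 50, or 50 and over). Age is a covariate in the primary ANCOVA (SAP 13.1.1), the random-coefficient model and the imputation regressions (SAP 13.1.2). The SAP's MMRM adjusts for pre-treatment slope and baseline score only, and its Cox model for EDSS-plus (SAP 13.2) contains treatment only. Protocol 11.2 has baseline age in both.

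**Imputation.** Both multiple imputations (SAP 13.1.2, with the same text in Protocol 11.2) begin with a Month 3 CombiWISE score. SAP 4.2 and the Protocol 25.1 flow chart schedule the score after baseline only at Months 6, 12, 18 and 24. After imputation under missing at random (MAR), the SAP fits the random-coefficient model and names no contrast. For the missing-not-at-random (MNAR) copy-reference version it names no analysis model.

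**The concern.** An intercept has no meaning until time zero is fixed. Protocol 11.2 associates a lower intercept with repair, so an origin well before treatment could make pure slowing look like the opposite of repair, or hide a real early improvement.

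The primary endpoint is an AUC because, in the Figure 3 text, "comparing slopes would de-facto ignore the latter potentially important mechanism of action (MOA"). SAP 4.2 divides each patient's AUC by the square of that patient's own follow-up, so a dropout's observed months stand for the full two years. A missing-data sensitivity analysis should put that assumption to the test on the same AUC contrast. The only other AUC ANCOVA planned is the Completer rerun, which leaves dropouts out.

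Dropping the stratification factor from two models gives up precision in a trial of 66 patients.

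**Working it through.** **1. Intercept shift (exact).** Let the on-treatment line be a + b·t, with t in years from Month 0. At an origin D years earlier its intercept is a − b·D. If idebenone lowers the slope by δ and does nothing else, its on-treatment intercept exceeds placebo's by δ·D, which is worse because higher scores mean more disability. In units of one year's untreated progression, a 40% effect has δ = 0.40.

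- Origin at Month 0 (D = 0): shift 0.
- Origin at first visit, D = 1: shift 0.40 × 1 = 0.40.
- Both visits at the limits of the ±4-week window (Protocol 7.5.1): 56/365.25 = 0.15, so D runs from 0.85 to 1.15 and the shift from 0.34 to 0.46.
- D can be larger: "The trial started with a pre-treatment baseline period of at least 12 months" (SAP 3.2).
- Slowing plus a true step improvement of 0.40, D = 1: −0.40 + 0.40 = 0, so the step vanishes from the intercept.

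For the SAP's own four-intercept hypothesis under pure slowing, all four are equal at Month 0. With a first-visit origin, three are equal and the idebenone on-treatment one is higher by δ·D. The hypothesis is therefore true under one origin and false under the other. With δ = 0 the origin makes no difference, and slope contrasts never depend on it.

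**2. How often this would show (illustrative).** The documents give no figure for the intercept test. The power table (SAP 6.2) supplies a variance calibration, and it reproduces: with SD 46.2 and correlation 0.5, the SD of a difference is 46.2 × √(2 × 0.5) = 46.2, and 28 pairs with difference 25.62 give power 0.807, as stated. The trapezoid AUC over three half-yearly visits has mean 0.5 × slope and variance 0.25·s² + 0.875·r² (s = slope SD, r = residual SD). From 46.2/51.24 = 0.902, with slope set to 1, s² + 3.5·r² = 0.813. The split between s and r is not in the documents.

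A simulation used 33 per arm, 40% slowing, no step, linear progression, complete data, Month 0 score as covariate and age omitted. It tested the between-arm on-treatment intercept contrast, two-sided 5%, with 1000 replicates. Percentage of trials in which idebenone is significantly worse, first-visit origin:

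| Pre/post slope correlation | r = 0.10 | 0.20 | 0.30 | 0.40 | 0.46 |
|---|---|---|---|---|---|
| 0 | 41 | 41 | 38 | 34 | 31 |
| 0.5 | 42 | 40 | 37 | 30 | 30 |
| 1 | 40 | 36 | 35 | 33 | 31 |

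With a Month 0 origin it is 2% to 3%. With no drug effect it is 1.7% to 3.5% under either origin. With slowing plus the 0.40 step, idebenone is significantly better in 1.5% to 3.5% (first visit) against 58% to 100% (Month 0).

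Other assumptions change the rates. Taking 50% slowing, slope SD 2 and error SD 2, two-sided rejection with a Month −12 origin is 13.0% at an untreated slope of 2 points a year and 34.4% at 4. With a Month 0 origin it is 5.3% and 5.4%.

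**3. AUC contrast from the visit differences.** At scheduled visits, the scaled 0–24 month AUC weights the changes at Months 6, 12, 18 and 24 by 0.125, 0.125, 0.125 and 0.0625. A 0.40 step plus 40% slowing gives visit differences of 0.6, 0.8, 1.0 and 1.2, so the AUC effect is 0.125 × 2.4 + 0.0625 × 1.2 = 0.375. Slowing alone contributes 0.5 × 0.40 = 0.200, or 53%. A slope contrast therefore misses part of the effect, but a weighted sum of MMRM visit differences recovers all of it.

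**4. Noise in a dropout's scaled AUC.** Measurement-error variance with last visit at Month 6, 12, 18 or 24 is 2.00, 0.875, 0.420 or 0.242 × r². The Month 6 to Month 24 ratio is 2.00/0.242 = 8.3. Adding slope variance, the ratio of totals is (0.25·s² + 2.00·r²)/(0.25·s² + 0.242·r²). With the calibration above this is 1.09 at r = 0.10 and 6.36 at r = 0.46.

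**5. Age.** If age has residual correlation ρ with the outcome (assumed), leaving it out cuts the effective sample from 66 to 66 × (1 − ρ²): about 63, 60 or 55 for ρ = 0.2, 0.3 or 0.4.

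**The case against.** The SAP supersedes the protocol where they differ, and it names only an omnibus, non-directional test of four intercepts. The between-arm contrast and the first-visit origin are in the protocol alone, the contrast as an example. The Month wording in the SAP would even allow a Month 0 origin. This stands: the 30% to 42% rates describe the protocol's example contrast under an assumed variance split. They are not properties of the SAP test, whose rejection rate was not calculated. What survives is that the SAP leaves the origin open and its hypothesis changes truth value with it.

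The Figure 3 text argues for AUC. It is not a rule for reading this model, and the figure is not available. That also stands, and it limits how firmly anyone can say a worse intercept would be reported as failure to repair.

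A reader might infer that the primary contrast has no missing-data check at all. The documents do not support that. The planned MMRM gives visit differences under MAR, and step 3 shows that their weighted sum is the AUC contrast. The gap is mainly under MNAR.

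A reader might also take 8.3 as the excess variance of an early dropout. It counts measurement error only. The total ratio is about 1.1 to 6.4.

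Month 3 is best read as a drafting slip. With no score scheduled then, imputation can start only at Month 6, and no numerical effect has been shown. Omitting age is not shown to bias anything, since allocation is balanced within age strata.

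**Conclusion.** Three inexpensive corrections to sensitivity and secondary analyses are warranted. The primary ANCOVA, all slope contrasts and the no-effect case are untouched.

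- **Time origin.** The direction and size of the shift are exact for linear progression: drug effect × annual progression × years from origin to Month 0, or 0.40 of a year's progression for a 40% effect at one year. How often it would reach significance depends on assumptions.
- **Age.** Its absence from the SAP's MMRM and Cox models is plain in the text. The loss is precision, and its size rests on an age–outcome correlation that neither document gives. No figure is available for the Cox model.
- **Imputation.** Neither analysis re-estimates the scaled-AUC contrast, and the MNAR one is incomplete without a named model. The gain from adding it lies mainly under MNAR.

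It would be tempting to call these undeclared departures from the protocol. That cannot be judged: the SAP was written against protocol version 27, and the protocol available here is a later amendment.

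**What to change.** 1. Add baseline age to the SAP's MMRM and Cox models.
2. Define Time as (visit date − Month 0 visit date)/365.25 and use that one variable in every term of the random-coefficient models, including those for secondary endpoints.
3. Start sequential imputation at Month 6, and correct Month 3 in both documents. Under both MAR and copy-reference, run the scaled-AUC ANCOVA on each completed dataset and combine by Rubin's rules. Keep the random-coefficient model, with the on-treatment slope difference named as its contrast for both.
4. In SAP Section 16, list whichever of these items differ from protocol version 27.

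Protocol 7.6 says the data analysis has been completed. In that case the study report should state the time origin, first imputed visit, MNAR analysis model and covariates actually used, with reruns where they differ from the above.

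The cost is SAP wording and minor programming, or a rerun of existing programs and a note in the report. No new data are needed.
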